**B. Stop Dates**

- 1) If the year is unknown, then the date will not be imputed and will be assigned a missing value.
- 2) If the month is unknown, then assign ‘December.’
- 3) If the day is unknown, then assign the last day of the month.

**7.3 Software**

SAS® software version 9.2 or higher will be used to perform all statistical analyses.

## 8 STATISTICAL METHODS OF ANALYSIS

### 8.1 General Principles

Efficacy analyses will be based on the primary analysis set. GEE analysis ([Hanley et al. 2003](#)) for repeated measures will be performed to compare the two treatment groups with respect to the changes from baseline of primary endpoint, secondary endpoints, and all tertiary efficacy endpoints, using an exchangeable working covariance structure among time points. Baseline, gender and region will be included as covariates in the model. Compound symmetry may be used if convergence is not achieved or if the AIC is larger than the one from the exchangeable covariance structure.

In general, randomly missing efficacy data for an individual subject will be treated as missing. The GEE method might not adequately cover the projected decline for these subjects and may not be appropriately conservative. In such cases a single imputation method will be used to estimate the change in strength over the remaining time of the study as described in [Section 7.1](#) and these imputed values will be used for the GEE analysis. This method of imputation will be the primary analysis method for all repeated measures endpoints.

A sensitivity analysis without use of the single imputation method for dropouts will be also be performed using the same GEE model.

The statistical analyses will be reported using summary tables, figures, and data listings. Statistical tests will be 2-sided at the alpha =0.05 significance level. All analyses and tabulations will be performed using SAS®. Continuous variables will be summarized with means, standard deviations, standard errors, medians, minimums, and maximums. Categorical variables will be summarized by counts and by percentages of subjects in corresponding categories.

The final analysis will be conducted at Week 48.

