7.6.4.3 Tertiary Endpoints and Analysis

Analyses of tertiary endpoints will follow the same methods as the primary analyses of the primary endpoint, where data are available. The tertiary clinical efficacy analyses will assess the change from baseline for the SA-ER group compared to the placebo group using GEE for the following endpoints:

- UEC score based on percent predicted bilateral strength recorded in the upper extremity muscle groups
- LEC score based on percent predicted bilateral strength recorded in the upper extremity muscle groups
- Muscle strength (total force in kg) for each individual muscle group comprising the UEC and LEC
- Percent predicted muscle strength for each individual muscle group comprising the UEC and LEC using published normative data adjusted for age, gender, and weight
- Percent of predicted muscle strength in the knee extensors using published normative data adjusted for age, gender, and weight
- GNEM-FAS total score
- GNEM-FAS self-care domain score

- Health-related quality of life as measured by the INQoL, which will be reported as subscale scores with higher scores associated with more significantly diminished quality of life
- CGI-I scores
- CK levels in serum
- Trough (pre-dose) SA levels in serum (free) and urine (free, total, and bound; corrected for creatinine)

Additional details on the analysis of tertiary endpoints will be described in the SAP.

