For those early-withdraw subjects who are in the study for some period of time (defined as at least one non- missing post-baseline visit) but decline (defined as negative change from baseline to the last non-missing post-baseline visit), all missing post-baseline data will be imputed for the HHD efficacy endpoints such as UE, LE, and Knee extensors. The imputed values are calculated using the subject's average change at previous time points adjusted by the timing of missing data. For example, for a subject with only the first 2 data values the average of the existing values is taken and the rest are imputed by multiplying the average by the (duration of each missing)/(duration of last non missing). See [Table 7.1.1](#) for an upper extremity example.

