**Table 7.1.1: An example of the imputation method for a subject with only 2 values**

Week	Change from baseline	Average of existing data	Imputed values
8	-1		
16	-2		
		-1.5	
24	Missing		$-1.5 \times (24/16) = -2.25$
32	Missing		$-1.5 \times (32/16) = -3.00$
40	Missing		$-1.5 \times (40/16) = -3.75$
48	Missing		$-1.5 \times (48/16) = -4.50$

In order to avoid extreme cases of imputed values that would not reflect the clinical course of the disease, if any of the imputed values for a subject obtained using the proposed method yields values greater (in magnitude) than the worst observed decline of all other subjects at the imputed time point, then the worst observed decline of the other subjects at that time point will be used. This will be done separately for each treatment group.

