### 8.8.1 Analyses of Key Secondary Endpoints

Key secondary endpoints include the following:

- Lower Extremity Composite Score: Muscle strength based on MVIC against a dynamometer will be measured bilaterally in the following lower extremity muscle groups: knee flexors, hip flexors, hip extensors, hip abductors and hip adductors. The LEC is derived from the sum of the average of the right and left raw scores (measured in kg) at each time point through week 48.

- Muscle strength in the knee extensors: bilateral total force (in kg)
- GNEM Functional Activities Scale Mobility Domain score: this is a domain of the GNEM Functional Activities Scale reflective of lower extremity muscle strength

The LEC and Knee extensors will be analyzed in a similar fashion as the primary endpoint including sensitivity analyses as defined in Section 8.1.

Hochberg adjustment for multiplicity (Hochberg 1988) will be used for these three key secondary endpoints.

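### SAP 8.1 extends the dropout imputation to every repeated measures endpoint, but SAP 7.1 defines it for dynamometry only, so the GNEM-FAS Mobility analysis entering Hochberg can be read two ways

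*SAP*

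**What the plan says.** SAP 8.1 (General Principles) introduces a single imputation for dropouts, refers to Section 7.1 for the method, and closes with: "This method of imputation will be the primary analysis method for all repeated measures endpoints".

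SAP 7.1 (Handling of Missing and Incomplete Data) holds the rule itself. For a subject who leaves early after a decline, "all missing post-baseline data will be imputed for the HHD efficacy endpoints such as UE, LE, and Knee extensors". Decline is "defined as negative change from baseline to the last non-missing post-baseline visit". Each missing visit gets the subject's mean observed change, scaled by the week of that visit over the week of the last observed visit. If the result is more extreme than anything observed in the same treatment group, "then the worst observed decline of the other subjects at that time point will be used".

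SAP 8.8 says that secondary and tertiary endpoints follow the primary method, and assigns the 8.1 sensitivity analysis (the same GEE model without imputation) to the key secondary endpoints, with no exception. SAP 8.8.1 names only two of the three: "The LEC and Knee extensors will be analyzed in a similar fashion as the primary endpoint including sensitivity analyses". For Mobility it says only that the same GEE model is used. All three enter Hochberg.

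SAP 8.8.4 excludes sialic acid, creatine kinase and ManNAc from imputation. GNEM-FAS and INQoL have no such exclusion. Protocol 7.6.4.3 describes INQoL as scored "with higher scores associated with more significantly diminished quality of life".

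**The concern.** The scope sentence in 8.1 and the definition in 7.1 cannot both hold. A programmer following 8.1 imputes Mobility dropouts, and one following 7.1 does not. Hochberg works on the ranked p-values of all three key secondary endpoints, so the choice can also change the outcome for LEC and knee extensors. If it is made after unblinding, the reported key secondary results depend on a decision that was not fixed in advance.

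There is a second, conditional consequence. The trigger is a negative change, which means worsening for strength and for GNEM-FAS. On INQoL a negative change is improvement. Applied there, a rule meant to be conservative would project improvement for dropouts who improved and do nothing for those who got worse.

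**Working it through.** **1. How the sections treat a Mobility dropout**

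| Place | Implication |
|---|---|
| SAP 8.1, last sentence on imputation | Imputed |
| SAP 8.8, same methods as the primary endpoint | Imputed |
| SAP 8.8, no-imputation sensitivity analysis for key secondaries | Imputed (otherwise there is nothing to remove) |
| SAP 7.1, rule limited to HHD | Not imputed |
| SAP 8.8.1, sensitivity analysis names LEC and knee extensors | Not imputed |
| SAP 8.8.1, same GEE model for Mobility | Silent |
| SAP Appendix 10.2, missing GNEM-FAS items | Covers items within a visit, not dropout |

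The words *such as* in 7.1 can take in further dynamometry endpoints, but not GNEM-FAS or INQoL. The clause in SAP Section 1 that ranks the SAP above the protocol does not help, because the conflict lies inside the SAP.

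**2. The plan's own example (Table 7.1.1)**

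Imputed change at week w = mean observed change × w / last observed week, if the last observed change is below 0. With -1 at Week 8 and -2 at Week 16, the mean is -1.5:
- Week 24: -1.5 × 24/16 = -2.25
- Week 32: -1.5 × 32/16 = -3.00
- Week 40: -1.5 × 40/16 = -3.75
- Week 48: -1.5 × 48/16 = -4.50

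These match the table.

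**3. The same rule on Mobility (0 to 40, higher is better)**

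A dropout with -1 and -2 is carried to -4.50 at Week 48 under 8.1, beyond the 3.07-point MID in 8.8.1, unless the cap applies. Under 7.1 the value stays missing.

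Assume 40 subjects in an arm (80 randomized 1:1), k such dropouts, and a mean change of 0 in the others. The Week 48 arm mean then differs between the readings by k × (-4.50)/40:
- k = 2: -0.225
- k = 4: -0.45
- k = 6: -0.675
- k = 8: -0.90

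If the others change by -1 on average, the shift is k × (-4.50 + 1)/40, or -0.175 to -0.70. These are shifts in one arm. With a mean change of 0 in the others, each such dropout that one arm has in excess of the other moves the treatment difference by 4.50/40 = 0.1125 points. Equal numbers cancel.

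**4. Effect through Hochberg (assumed p-values)**

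Take LEC 0.045, knee extensors 0.03 and Mobility 0.04. The largest is 0.045 ≤ 0.05, so all three succeed. Now let Mobility be 0.06 under the other reading, with the rest unchanged: 0.06 > 0.05, 0.045 > 0.025 and 0.03 > 0.0167, so none succeeds.

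**5. INQoL, only if 8.1 is applied literally**

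- Changes of -4 (Week 8) and -8 (Week 16), both improvements: mean -6, and -6 × 48/16 = -18 at Week 48 before any cap.
- Last observed change +8, a worsening: not negative, so nothing is imputed.
- The cap does not correct this. With decline defined as negative, it limits imputed values to the largest observed improvement.

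A simulation gives a rough size. It assumes 40 per arm, between- and within-subject SD of 8 each, no true change, dropout after Week 16 unrelated to outcome, and the cap applied within arm. It uses simple Week 48 means, not the GEE model.
- At 10% dropout the placebo mean moves from -0.06 to -0.73.
- At 20% dropout it moves from -0.05 to -1.44.
- With equal dropout the between-arm difference is essentially unchanged.
- With 10% on placebo and 20% on SA-ER, the difference moves from 0.13 to -0.60, about -0.7 in favor of SA-ER. Simulation noise is about 0.1.

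**The case against.** The strongest reply is that the intended scope is clear enough. SAP 8.1 defines no rule of its own. Just before the disputed sentence it speaks of imputing change in strength and refers to 7.1, where the rule covers dynamometry. The two key secondary endpoints named in 8.8.1 are exactly those that 7.1 imputes. On this view the 8.1 sentence and the general sensitivity sentence in 8.8 are loosely worded. That is a fair account of what was probably meant, and it decides which way the repair should go. It does not remove the conflict: 8.1 says in terms that the imputation is primary for all repeated measures endpoints, and 8.8 supports it.

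The reply does stand against several stronger readings that a reader might infer:

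- *The SAP specifies two primary analyses of Mobility.* It does not. It specifies one GEE analysis whose imputation scope is unclear. The two sets of Mobility analyses in 8.8.1 (with and without subjects at the maximum baseline score) are a separate matter.
- *The SAP imputes INQoL in the wrong direction.* That follows only if the last sentence of 8.1 overrides the section it cites. Under 7.1, INQoL is not imputed at all. It is also tertiary, with nominal p-values.
- *The protocol confirms the broad scope.* Protocol 7.6.4 has a similar sentence, but without the word imputation. In the synopsis the same sentence directly follows the GEE description, where no imputation is mentioned, so it refers to GEE. In 7.6.4 imputation text stands in between and the reference is ambiguous. Protocol 7.6.4.1 again ties imputation to change in strength.
- *Mobility should be added to the sensitivity list in 8.8.1.* If Mobility is not imputed, that analysis would simply repeat its primary analysis.

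**Conclusion.** The point holds as a conflict between stated rules within the SAP. For GNEM-FAS Mobility, 8.1 and 8.8 lead to imputation of declining dropouts, and 7.1 and 8.8.1 lead to none. The p-value that enters Hochberg depends on which is followed.

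The size cannot be predicted, because the documents give no dropout rate. The 0.23 to 0.90 point range rests on 2 to 8 identical dropouts, no mean change in the others and no binding cap. The Hochberg example shows that a reversal is possible, not that it is likely. The INQoL direction error is real under a literal reading of 8.1 and absent under 7.1. The primary endpoint is not touched, since UEC is imputed on either reading. This should be settled before unblinding.

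**What to change.** - **SAP 8.1.** Replace the disputed sentence with: *The Section 7.1 dropout imputation is the primary method for the HHD (dynamometry) endpoints only; GNEM-FAS, INQoL and all other endpoints use the GEE model without dropout imputation (item-level scoring rules in the appendices still apply).* Naming HHD endpoints as a class keeps the open wording of 7.1, and the sentence agrees with 8.8.4.
- **SAP 8.8.** Limit the no-imputation sensitivity analysis among the secondary endpoints to LEC and knee extensors, to match 8.8.1. Do not add Mobility to it.
- **If any non-HHD endpoint is to be imputed after all.** Name it, and define both decline and the cap in the worsening direction of its scale.

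The cost is a few sentences in the SAP. No data collection, sample size or primary analysis changes.

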### 8.2 Visit Window Definition

Unscheduled visit occurring prior to or on the date of initiation of the first dose will be mapped to the baseline visit if it is the latest assessment prior to or on the date of initiation of the first dose; otherwise no mapping will be performed.

Unscheduled visit and early termination visits occurring after the date of initiation of the first dose will be mapped to the closest post-baseline scheduled visit according to [Table 8.2.1](#). If the unscheduled visit is in the middle of two scheduled visits, map to the later one.

When there are more than one measurements mapped to the same scheduled visit (including the original measurement taken from the scheduled visit), the measurement taken on the scheduled visit will be used if it is not missing, otherwise the one closest to the target day will be used. If more than one visit has the equal distance to the target day then the later one

will be used. If more than one measurement collected on the same day, use the time or the sequence number to select the latest record.

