SUICIDAL IDEATION AND BEHAVIOR ^j	X	X		X	X	X	X	X	X	

ASSESSMENTS AND EVENTS*	SCREENING ^a	BASELINE ^a	TREATMENT PERIOD ^b							SAFETY FOLLOW-UP ^c
	WEEK -4 to -1	0	4 (TC)	8	16	24	32	40	48/ET ^a	52 (TC)
ADVERSE EVENTS	X	X	X ^b	X	X	X	X	X	X	X
TREATMENT DISPENSED ^k		X		X	X	X	X	X		
TREATMENT COMPLIANCE				X	X	X	X	X	X	

* Refer to Study Reference Manual for recommended timing and order of assessments to be administered at each study visit

- a. Potential subjects will be screened approximately seven days (up to 28 days) before the Baseline Visit. Study drug will be dispensed only after all study procedures at the Baseline Visit have been performed. For subjects who discontinue prior to completing the study, every reasonable effort should be made to perform the Early Termination (ET) procedures within four weeks of discontinuation.
- b. Visits occur every 8 weeks ± 5 days; subjects will be contacted by telephone call (TC) at Week 4 for abbreviated safety assessment. Additional unscheduled telephone calls may also occur for subject follow up. Unscheduled visits are allowed for safety or administrative purposes. Notify the medical monitor before an unscheduled visit.
- c. To be completed only for subjects who complete the study and choose not to enroll in the extension study, UX001-CL302, or who discontinue the study early. This call is not required for subjects who are eligible and choose to take part in the extension study, UX001-CL302. The site personnel will initiate a safety follow-up telephone call 28 days (+5 days) after a subject's last dose of study drug to collect information on any ongoing or new AEs, serious adverse events (SAEs), and concomitant medications. Appropriate follow-up should continue until all safety concerns, in the Investigator's opinion, are resolved.
- d. Medical history will include a detailed GNEM disease-specific medical history.
- e. CGI-Severity scale will be assessed at Baseline (Week 0) along with identification of 3 target areas for disease improvement; CGI-Improvement scale will be assessed at each subsequent visit using 3 target areas identified at Baseline.
- f. Pre-dose blood samples and first-morning void urine will be collected to assess trough SA levels; record volume of urine collected.
- g. An aliquot from the urine sample provided for the standard urinalysis will be used for assessment of ManNAc.

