5 INTRODUCTION

The product under investigation is sialic acid (SA) administered in extended release (SA-ER) tablets. SA-ER is intended for use as a substrate replacement therapy for the treatment of GNE myopathy (GNEM), also known as Hereditary Inclusion Body Myopathy (HIBM), Quadriceps Sparing Myopathy (QSM), Inclusion Body Myopathy type 2, Distal Myopathy with Rimmed Vacuoles (DMRV), and Nonaka myopathy (Huizing et al. 2009); (Jay et al. 2009); (Malicdan et al. 2008). Currently there are no approved treatments for GNEM.

SA is an essential, naturally occurring amino sugar found in humans and most organisms. Defects in the SA biosynthetic pathway cause GNEM, a severe progressive myopathy. By replacing SA substrate, sialylation should be restored on key target glycoproteins and glycolipids, leading to restoration of biochemical function, improved muscle physiology and improved clinical function. The scientific rationale is primarily based on the nature of the underlying genetic defect supported by proof of concept work in a knockout mouse that models the muscle disease and pathology of HIBM (Malicdan et al. 2009). The safety of SA has been studied in chronic treatment studies in HIBM mice and toxicology studies in multiple species of normal animals. These data demonstrated reasonable safety for SA and established a no adverse effect level (NOAEL) of 2,000 mg/kg in rats and dogs, enabling clinical studies in GNEM patients.

Ultragenyx has developed SA-ER tablets since successful use of SA replacement therapy in humans is believed to depend upon optimized exposure to the compound. SA has a half-life of less than 1 hour in the circulation (Malicdan et al. 2009). SA-ER was developed to improve the stability of exposure to SA and allow more appropriate dosing and efficient substrate replacement. The SA-ER formulation was evaluated in an initial Phase 1 study to establish the safety and pharmacokinetic (PK) profile of a single dose and 7 days of repeat dosing in SA-deficient GNEM patients. The study drug was well tolerated at all dose levels. There were no serious adverse events (SAEs), and all adverse events (AEs) were mild to moderate with no dose relationship or pattern.

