5.2.3 Previous Clinical Studies

Key results from studies to support the use of SA in treating GNEM are summarized below; additional details may be found in the IB.

Phase 1 Pharmacokinetic and Safety Study (UX001-CL101): A Phase 1 study to evaluate the safety and PK of single and repeat doses of SA-ER tablets was conducted in GNEM subjects. Twenty-seven (27) subjects were assigned to treatment; 26 were dosed with SA-ER and completed dosing. Subjects received SA-ER tablets orally at one of five dose levels (650 – 6000 mg) in the single dose phase (fasting and fed), and one of four dose levels in the repeat dose phase (1950 – 6000 mg/day divided into three equal doses).

PK analysis showed acceptable absorption of the product with SA exposure that covered about 8-16 hours. Repeat dosing for 7 days with SA-ER showed that trough levels could be maintained above the pre-dose baseline level, as expected for a sustained release formulation.

SA-ER was well tolerated in this group of GNEM patients based on the AE profile, the absence of SAEs, and the lack of treatment emergent changes in any parameter (AEs, physical examinations, vital signs and clinical laboratory evaluations). The AE profile was unremarkable; the most common treatment-emergent adverse event (TEAE) reported was headache. However, there was no dose-dependent pattern for any drug-related or unrelated event.

Phase 2 Pharmacokinetic, Pharmacodynamic and Safety Study (UX001-CL201):

A Phase 2 randomized, double-blind, placebo-controlled, parallel group study was conducted to evaluate the dose and PD of SA-ER tablets in 47 GNEM patients (Argov et al. 2014). Subjects were randomized to receive placebo or 3 g/day or 6 g/day SA-ER. After 24 weeks, placebo subjects crossed over (blinded) to either 3 g/day or 6 g/day SA-ER for an additional 24 weeks. Assessments included drug concentration measurements, upper extremity composite (UEC) and lower extremity composite (LEC) muscle strength scores, other clinical endpoints, patient reported outcomes, and safety.

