7.5.1.4 End of Study/Early Termination Visit (Week 48/ET)

All randomized subjects who complete the study or discontinue early should complete the Week 48/ET visit.

For subjects who discontinue prior to completing the 48-week Treatment Period, every reasonable effort should be made to perform the Early Termination Visit procedures within four weeks of discontinuation.

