7.5.3 Drug Concentration Measurements

The concentration of free SA in serum will be measured. At the Baseline Visit and each subsequent visit a serum sample will be collected prior to the morning dose of study medication (pre-dose) to assess trough levels of free SA.

The free, total, and bound urine SA levels (corrected for creatinine) will be measured. At the Baseline, and Week 16, 32, and 48 (or Early Termination) visits, first-morning void urine will be collected (pre-dose) to assess trough levels; the volume obtained will be recorded.

Collection and processing instructions can be found in the Laboratory Manual.

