#### 8.8.4 Analyses of Sialic Acid, Creatine Kinase and Free ManNAc

The following clinical lab outcomes will be analyzed using GEE using the SA analysis set. No imputation will be performed for missing data. Free, total, and bound urine SA and urine ManNAc are collected at Baseline, Week 24, and Week 48. All other labs are collected every 8 weeks up to Week 48.

- Free SA: Free SA levels in serum assess the drug concentration in the bloodstream resulting from treatment and are the best indicator of compliance with the treatment regimen. Free SA levels in serum are expressed in micrograms of SA per ml of serum
- Free SA in urine: Free SA levels in urine will be assessed to determine the overall absorption of SA-ER over time. Free SA levels in urine will be expressed in micrograms of SA per ml of urine.

- Total SA in urine: Total SA levels in urine will be assessed to determine the accumulated excretion of sialic acid from dosing. Total SA levels in urine will be expressed in micrograms of SA per ml of urine.
- Bound Sialic Acid in urine: Bound SA levels in urine is calculated as the difference between each subject's total sialic acid and free sialic acid in urine corrected for total protein. Bound sialic acid in urine may also be corrected for creatine and calculated as the difference between each subject's total sialic acid and free sialic acid corrected for creatine. The primary correction for SA will be total protein with creatine correction only used when an alternate method is required
- Creatine Kinase Levels: CK levels in serum will be measured to assess the degree of reduction of CK levels observed as a surrogate for muscle injury.
- Free ManNAc in urine: Free ManNAc levels in urine will be assessed to determine the amount of naturally occurring ManNAc in the urine of study subjects and the stability of these levels over time. Free ManNAc levels in urine will be expressed in micrograms of SA per ml of urine. Changes from baseline in Free ManNAc levels in urine will be analyzed.
- Free ManNAc/Free SA in urine: The ratio of free ManNAc to free SA levels in urine will be assessed to ensure compliance with the restriction placed on ManNAc consumption during the study period.

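### Sialic acid samples from early-termination visits, drawn days to weeks after study drug has stopped, can enter the SA analysis as if they were pre-dose troughs (minor)

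*SAP*

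**What the plan says.** **Visit timing.** Protocol 7.5.1.4 applies the final visit to early discontinuers: "All randomized subjects who complete the study or discontinue early should complete the Week 48/ET visit". For them, "every reasonable effort should be made to perform the Early Termination Visit procedures within four weeks of discontinuation". Four weeks is a best-effort target counted from discontinuation. It is neither a hard limit nor counted from the last dose.

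**Sampling.** Protocol Table 2.1 and Section 7.5.3 place serum free SA at every clinic visit and urine SA at Weeks 16, 32 and 48 or early termination. Both are described as pre-dose trough samples. Protocol 7.6.5 likewise plans the SA analysis at trough.

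**Mapping.** SAP 8.2: "Unscheduled visit and early termination visits occurring after the date of initiation of the first dose will be mapped to the closest post-baseline scheduled visit". Table 8.2.1 gives the windows by study day, and the Week 48 window is open-ended from Day 310. A non-missing value from the scheduled visit takes priority over any other value in the same window.

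**Analysis.** SAP 8.8.4 analyses SA by GEE in the SA analysis set, without imputation. It gives the serum variable this meaning: "Free SA levels in serum assess the drug concentration in the bloodstream resulting from treatment". It also calls serum free SA the best indicator of compliance with the regimen. The SA analysis set (SAP 6.4) admits a subject who has an evaluable serum level at any time point; evaluable is not defined.

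**Kinetics.** Protocol Section 5: "SA has a half-life of less than 1 hour in the circulation". Protocol 5.2.3: "PK analysis showed acceptable absorption of the product with SA exposure that covered about 8-16 hours".

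**The concern.** The variable is defined as a trough under dosing. Once dosing has stopped for good there is no trough, and after the tablet's exposure has passed a serum sample shows only the subject's own SA. Nothing in SAP 8.2, 8.8.4 or 6.4 separates such samples from true troughs.

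This differs from strength or function, where a value after stopping can belong in a treatment-policy comparison. A drug concentration after stopping says nothing about what the regimen delivered.

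At stake is the serum SA contrast between the arms. Off-drug samples leave placebo values unchanged and pull SA-ER values back towards baseline, so the bias runs towards no difference. The contrast matters most if the UEC result is weak, because it helps separate poor exposure from lack of effect.

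**Working it through.** The plan states no figure for this point, so the check has three steps.

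**1. Is the sample off drug?** Inputs are the half-life under 1 hour (Protocol 5), exposure of about 8-16 hours (Protocol 5.2.3) and the four-week target (Protocol 7.5.1.4).
- Four weeks: 28 × 24 = 672 h, which is at least 672 circulating half-lives. For an extended-release tablet the exposure period is the fairer yardstick: 672 / 16 = 42 times its upper end.
- One week: 7 × 24 = 168 h; 168 / 16 = 10.5 times the upper end.
- Over-generous check, treating 16 h as if it were a half-life: the residual is 2^(-168/16) = 0.07% at one week and 2^(-672/16), about 2 × 10^-13, at four weeks.

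**2. Does the sample reach the analysis?** It does only if no scheduled value lies in the same window. Assume scheduled visits fall on their target days and are attended up to the last dose. Take last-dose days 1 to 336 as equally likely, with the early-termination visit L days later (L from 1 to 28).
- The Week 8 window is otherwise empty for 56 last-dose days (Days 1-56).
- Each of the five later windows is otherwise empty for 27 + L last-dose days. For Week 16, for example, these are Days 86 − L to 112.
- Share = [56 + 5 × (27 + L)] / 336.

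| Lag L (days) | Share of last-dose days for which the sample fills an empty window |
|---|---|
| 1 | 196/336 = 58% |
| 7 | 226/336 = 67% |
| 14 | 261/336 = 78% |
| 28 | 331/336 = 98.5% |

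Examples at L = 28: last dose Day 60, visit Day 88, mapped to Week 16; last dose Day 300, visit Day 328, mapped to Week 48. The scheduled-value rule therefore reduces the problem but does not remove it.

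**3. How large is the bias?** Assume that an off-drug SA-ER serum sample has a change from baseline of about 0. With d such samples among n, the SA-ER mean change is diluted by d/n. About 80 subjects randomised 1:1 give n of about 40 at one visit, and 40 × 6 = 240 over six post-baseline serum visits.

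The documents plan no dropout rate. Protocol 5.2.3 reports 47 subjects in the 48-week Phase 2 study, of whom 46 entered the extension after completing it. At most 1/47 = 2.1% stopped early; 40 × 1/47 = 0.85, so about one SA-ER subject.

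| Scenario | Off-drug values d | All at one visit, d/40 | Across six visits, d/240 |
|---|---|---|---|
| Phase 2 rate | 1 | 2.5% | 0.4% |
| Assumed 4 stoppers, half contribute | 2 | 5% | 0.8% |
| Assumed 8 stoppers, half contribute | 4 | 10% | 1.7% |

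The half is an assumption and lies below the shares in step 2. If all 8 contributed, the figures would be 8/40 = 20% and 8/240 = 3.3%, but the first of these needs a fifth of the arm to stop and every sample to fall at the same visit. SAP 8.8.4 does not say whether the SA contrast is read at one visit or across visits, so both columns are shown.

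**The case against.** The strongest reply is that this touches very little. The Phase 2 completion record suggests about one affected subject. An early stopper's scheduled on-drug samples stay in the analysis, and a scheduled value overrides an early-termination value in the same window. Protocol 7.5.3 and 7.6.5 show that a pre-dose trough was intended, so the gap can be called one of clarification. Amendment 5 already says urinary SA will have limited use. All of this stands, and it is why the point is minor. It does not close the gap: no stated rule removes an off-drug sample, and the word evaluable in SAP 6.4 admits subjects and does not screen individual samples.

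Two objections bear on the remedy and are accepted. The documents do not say that the time of the last dose is recorded, so a cut-off in hours may not be programmable. The half-life and the 8-16 hours describe SA exposure from the circulation, and neither gives a washout time for urinary SA, least of all bound SA. An off-drug change of about 0 is therefore not established for urine.

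A reader might also infer that a subject who took every dose until stopping would be classed as non-compliant. The documents do not support this. SAP 5.2 computes compliance as dosage received over dosage planned, with planned dosage counted only up to withdrawal, and the Per Protocol Set (SAP 6.2) uses that figure. Protocol 7.4.7 says only that SA levels may be used to estimate compliance.

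**Conclusion.** The concern holds as a minor point. As written, the plan can pool off-drug serum SA values with pre-dose troughs, and the resulting bias in the SA-ER versus placebo contrast is towards zero. The expected size is about 2.5% of the SA-ER mean change at one visit, or 0.4% across six, at the Phase 2 dropout rate. Under an assumed 4-8 early stoppers with 2-4 off-drug values it is up to 5-10% if they cluster at one visit, and about 1-2% if spread. These figures rest on an off-drug change of about 0, on 40 SA-ER subjects per visit, and on dropout assumptions that the plan does not supply.

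It might be inferred that the trial loses its evidence of drug delivery, or that the efficacy result is compromised. Neither follows. Serum SA is drawn at six post-baseline visits, on-drug samples are retained, and tablet accountability (Protocol 7.4.7) gives separate evidence of intake. The primary UEC test, dose-based compliance and the Per Protocol Set do not use these values. The SAP also does not label the samples on-treatment; it simply makes no distinction.

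**What to change.** Add to SAP 8.8.4:
- For subjects who have permanently discontinued study drug, serum free SA samples collected more than one calendar day after the last-dose date are excluded from the by-visit summaries and the GEE of SA levels, and are listed separately.
- Urine SA samples collected after that point are flagged in the same way, and the urine analysis is shown with and without them.

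The rule needs only a date. A sample on the morning after a bedtime dose is kept. The first excluded day begins at least 24 h after the last dose (from the end of day D to the start of day D + 2), beyond the 8-16 h of exposure. Limiting the rule to permanent discontinuation keeps samples from subjects who merely missed doses.

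Leave the SAP 8.2 mapping unchanged for efficacy and safety endpoints, and do not extend the exclusion to creatine kinase or ManNAc, which share Section 8.8.4.

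The cost is two sentences, one programming flag and one repeated urine analysis. The last-dose date is already needed to time the safety call (Protocol 7.5.1.5). The downside is a few fewer SA observations.
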